#### 4.2. Study Design Rationale

The single-masked, randomized 2x2 cross-over design will be used to allow for each subject to be his/her own control. Furthermore, it is also desirable that the study encompass a variety of subjects wearing diverse brands or materials as well as different modalities of soft, spherical contact lenses, as the investigational product is intended to be compatible with all soft contact lens materials. Given a large distribution of possible types or brands, or materials of contact lenses, a crossover study was deemed to be more relevant and applicable to investigate the potential outcomes.

In addition to visual acuity investigation, this study will also be useful to explore the impact of the artificial tears to the fitting of subjects' own habitual contact lenses which also merits a crossover design. Moreover a previous study using the same marketed eyedrop as a control, employed a crossover design with a 90-minute washout to document the effects of lubricating eyedrops on low contrast LogMAR visual acuity.

#### 4.3. Enrollment Target and Study Duration

A total of up to 45 subjects will be enrolled (informed consent signed) and the eyedrop application randomized in up to 3 clinical sites in the US. The goal is for a sample size of 38 subjects after subjects who withdraw or are discontinued. The Investigator is responsible for ensuring that all subjects entering the study conform to subject selection criteria. The number of subjects targeted for randomization and completion are as follows:

	Total
Randomization	45
Completion	38
Number of sites	3
Number of subjects per site	15

Table 1: Target number of subjects by site

The study will last approximately 1.5 months and includes an approximately 1-month enrollment period. Once the informed consent has been signed the subject will be considered enrolled. An additional subject may be enrolled if a subject discontinues from the study prematurely. Subjects who are discontinued prior to the final evaluation may be replaced at the discretion of the study sponsor. The investigation will end at the time that the study data is hard locked.

#### 5. TEST ARTICLE ALLOCATION AND MASKING

#### 5.1. Test Article Allocation

Subjects will be randomly assigned to one of two unique sequence groups (Test/Control and Control/Test) to bilaterally receive two different test articles i.e., one investigational formulation in a Novelia® eyedropper and another marketed Blink® Tears eyedrops, one at a time over the same visit (Table 2).

Table 2. S	Subject	assignment	to	treatments	(eye d	rops)
------------	---------	------------	----	------------	--------	-------

Sequence of treatments	Visit 1 – Period 1	Visit 1 – Period 2
Sequence 1	Test	Control
Sequence 2	Control	Test

The randomization scheme will be generated using the PROC PLAN procedure from the Statistical Analysis System (SAS) Software version 9.4 or higher. The study site will follow the randomization scheme provided and will complete enrollment according to the randomization list and will not pre-select or assign subjects. The assignment of the subjects must be performed after baseline evaluation. The following must have occurred prior to randomization:

- Informed consent has been obtained
- Subject meets all the inclusion / exclusion criteria
- Subject history and baseline information has been collected

When dispensing test articles, the following steps should be followed to maintain randomization codes:

- 1. Investigator or designee (documented on the Delegation Log) will consult the randomization schedule to obtain the test article assignment for that subject prior to dispensing.
- 2. Investigator or designee will record the subject's number on the appropriate line of the schedule.
- 3. Investigator or designee will pull the appropriate test articles from the study supply. All test articles that are opened, whether dispensed (placed on eye or dispensed outside the clinical site) or not, must be recorded on the Test Article Accountability Log in the "Dispensed" section.

#### 5.2. Masking

Masking will be used to reduce potential bias. Due to the difference in the shape of the eyedroppers, double masking will not be possible. However, the subjects will be masked from the identity of the lubricating eye drops. The identity of the investigational products will be masked by over labeling the eye drop bottles with a label containing the study number, expiration date and the randomization codes. Investigators and clinical site personnel involved in the data collection will not be masked as to the identity of the investigational product.

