#### 1.2. Intended Use of Investigational Products

The investigational eye drops are developed as preservative-free lubricating eye drops, and the other product, the control drop is CE approved and is a marketed eye drop, available over the counter (without a prescription) in the US.

The intended use of the study artificial tears is treatment of subjects with symptoms of ocular dryness. The indications for the investigational eyedrops are consistent with 21 CFR Part 349.60 pertaining to the demulcent eyedrops as per the FDA OTC monograph. The following are the indications:

- For the temporary relief of burning and irritation due to dryness of the eye.
- For the temporary relief of discomfort due to minor irritation of the eye or to exposure to wind or sun.
- For use as a protectant against further irritation or to relieve dryness of eye.
- For use as a lubricant to prevent further irritation or relieve dryness of the eye.

In this study, the test articles will be used over the soft spherical contact lenses in a non-dispensing modality to assess visual acuity after instillation to support EU registration. In the EU, the eyedrops will be intended to be used with contact lens wear.

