#### 6.4. Packaging and Labeling

The test articles will be packaged in bottles as the primary packaging. The test article will be over-labeled to mask the subject to the identity of the eyedrops. The test articles will be in plastic bags as the secondary packaging form. The sample study label is shown below:

For Use in Clinical Study CR-6503 EYE DROPS CAUTION - For Investigational Use Only Use in accordance with the instructions provided Net Contents: 0.34 to 0.5 FL 0Z (10-15mL) STERILE Store at Room Temperature Sponsored by: Johnson & Johnson Surgical Vision, Inc. Irvine, CA 92618 USA LOT:ABC123 EXP: 2023/09/30 RC: S

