1.10	Remove Habitual Contact Lenses	Remove habitual contact lenses and store in a case with non-preserved saline.	
1.11	Slit Lamp Biomicroscopy	The FDA slit lamp classification scale will be used to grade the findings and determine eligibility. If there are any Grade 3 or higher other slit-lamp findings, the subject is ineligible to continue at this time, but may return up to one additional time to determine eligibility. If discontinued a final examination must be completed. If there are no slit lamp findings, and the clearance of the fluorescein needs to be expedited, preservative- free saline may be instilled.	

	Visit 1: Baseline			
Step	Procedure	Details		
1.12	Expanded Sodium Fluorescein Corneal Staining	Corneal Staining Assessment (FDA grading scale) will be assessed using a more detailed scale for internal purposes only.		
1.13	Eligibility After Baseline	All responses to Inclusion Criteria questions must be answered "yes" and all responses to Exclusion Criteria questions must be answered "no" for the subject to be considered eligible.		
1.14	Re-insert Habitual Lenses	Habitual Lenses will be re-inserted.		
1.15	Settling Time	Allow habitual lenses 5 minutes to settle.		
1.16	Baseline Distance ETDRS LogMAR Visual Acuity	
 
Under high illumination and high chart luminance, record the distance (4 meter) ETDRS low contrast visual acuity OD (LC1) and OS (LC2). Note:
 
The room illuminance must be between 7.3 and 7.9 EV (394-597 lux).
 
Distance Low Contrast chart luminance acceptable range between 10.5 -10.7 EV (181-208cd/m^2)
 
		

	Visit 1: Treatment 1			
Step	Procedure	Details		
1.17	Randomization and Drop Selection	Assign the first study drop (Drop#1) based on the randomization schedule.		
1.18	Drop Instillation	The investigator will break the seal of drop #1 and discard the first drop. The investigator or technician will instill 1 drop in the right eye. Wait 1 minute and then instill 1 drop in the left eye.		
1.19	Subject Reported Ocular Symptoms	Subjects will respond to a verbal open-ended symptoms questionnaire.		
1.20	Drop Settling	Allow the drops to settle for 3 minutes (from OD drop #1 administration).		
1.21	3-minute Distance ETDRS LogMAR Visual Acuity (From OD Drop #1 Administration Time)	Under high illumination and high chart luminance, record the distance (4 meter) ETDRS low contrast visual acuity OD (LC3) and OS (LC4).		

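### Subject masking rests on an over-label that does not hide the eyedropper shape, and no written step keeps the dropper out of the subject's view, so the only masking the trial claims is not assured.

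*Combined protocol and SAP*

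**What the plan says.** Section 5.2 of the protocol opens with the obstacle: "Due to the difference in the shape of the eyedroppers, double masking will not be possible". It then claims masking for one party only: "However, the subjects will be masked from the identity of the lubricating eye drops". The method follows: "The identity of the investigational products will be masked by over labeling the eye drop bottles with a label", the label carrying the study number, expiration date and randomization codes. The section is open about everyone else: "Investigators and clinical site personnel involved in the data collection will not be masked as to the identity of the investigational product".

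Section 6.4 repeats the same device, "The test article will be over-labeled to mask the subject to the identity of the eyedrops", and Table 3 lists both products as over-labelled. No other subject-masking measure appears.

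Section 7.2 describes the handling. In step 1.18, "The investigator will break the seal of drop #1 and discard the first drop", and then "The investigator or technician will instill 1 drop in the right eye", with the left eye a minute later. Step 1.25 repeats this for the second product. Neither step says where the bottle is opened, whether the subject can see it, or where the subject looks.

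Section 5.3, on maintaining and breaking the mask, deals with emergency unmasking and with not revealing assignment to site or sponsor personnel. It does not tell staff to withhold product identity from the subject.

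**The concern.** The stated method does not address the stated obstacle. Section 5.2 names shape as what prevents double masking, and a label covers printing, not shape.

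The design gives subjects an opportunity to compare. Each receives both products in one visit, with a washout of at least 90 minutes between them. Section 1.2 says the control "is a marketed eye drop, available over the counter (without a prescription) in the US", the sites are in the US, and exclusion criterion 8 exempts users of artificial tears. A subject who knows the retail bottle could identify the control and deduce that the other is the new product.

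What is at stake is the primary endpoint and the symptom data. Low-contrast acuity is obtained from the subject's own reading of the chart, and ocular symptoms are collected by open-ended questioning. Success of this confirmatory study depends on a single non-inferiority comparison (section 14.5). Because the staff who collect the data are unmasked, the subject's mask is the only one in place.

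**Working it through.** **Text check.** The passages, set side by side:

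| Question | Where | What is written |
|---|---|---|
| Why is double masking impossible? | 5.2 | Eyedropper shapes differ |
| Who is masked? | 5.2 | Subjects only |
| By what means? | 5.2, 6.4, Table 3 | Over-label |
| Is the dropper hidden at opening or instillation? | 7.2, steps 1.18 and 1.25 | Nothing stated |
| Are staff told not to disclose identity to the subject? | 5.2, 5.3 | Nothing stated |

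The gap follows from the text and needs no arithmetic.

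**Scale of the primary test.** Inputs from section 14.2: within-eye covariance matrix with variances 0.005117 and 0.005213 and covariance 0.003170; margin 0.05 logMAR; assumed true difference 0.025 logMAR; 38 completers, hence 38 × 2 = 76 eyes; two-sided alpha 0.05. The subject intercept (0.003322) cancels in the within-eye difference.

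- Variance of the within-eye difference: 0.005117 + 0.005213 − 2 × 0.003170 = 0.00399.
- SE with 76 eyes, taking the eyes' differences as independent: √(0.00399/76) = 0.00725.
- Noncentrality: (0.05 − 0.025)/0.00725 = 3.45.
- Power: 91.9% from a noncentral F with 37 df, 93.2% by normal approximation. Table 10 states 91%, so this SE is a fair reconstruction of the plan's own basis.
- One difference per subject instead gives SE √(0.00399/38) = 0.01025 and power of only 66% to 68%, so the plan's figure counts both eyes.

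**Illustration of a bias.** The documents give no size for an expectation effect, so the average shift b, taken over all subjects, is an assumption and is shown as a range. The low end, 0.002, corresponds for example to one subject in five shifting by 0.01 (0.2 × 0.01). With SE 0.00725 and the normal approximation:

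- b favouring test, true difference at the margin: probability of declaring non-inferiority = Φ(−1.96 + b/SE).
- b against test, true difference 0.025: power = Φ((0.025 − b)/SE − 1.96).

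| b (logMAR) | b/SE | Error at the margin, bias favours test | Power, bias against test |
|---|---|---|---|
| 0 | 0 | 2.5% | 93.2% |
| 0.002 | 0.28 | 4.6% | 88.8% |
| 0.005 | 0.69 | 10.2% | 78.8% |
| 0.01 | 1.38 | 28.1% | 54.4% |

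With 37 df the last two rows become 9.9% and 26.9% for error, and 76.7% and 52.2% for power. If each subject's two eyes moved fully together (SE 0.01025), the error would be 3.9% at b = 0.002 and 16.3% at b = 0.01.

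**The case against.** A reader might infer that subjects can see which drop they are given, so that the mask has failed. The documents do not support that. Staff open the bottle and instil the drop, and nothing says the bottle is in the subject's view. Silence leaves the mask unassured; it does not show that it is broken.

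Nor is noticing two shapes the same as knowing which is test. Section 5.2 claims to mask identity, not the fact that the droppers differ. Staff have the randomization schedule and subjects do not, and the sample label in 6.4 shows no brand name. Recognition of the retail bottle is possible but not established: the documents do not describe its shape or say how many subjects will have used it, and a user of artificial tears need not use this brand.

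The figures have limits too. The shift is assumed, its direction is unknown, and partial recognition would pull the average towards the low end. The content of the logMAR procedure in Appendix D is not visible in the copy reviewed, so how far it limits the influence of a subject's effort or guessing cannot be judged here.

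Finally, unmasked staff record every acuity. Section 5.2 discloses this, and hiding the dropper from the subject would not cure it.

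All of this stands and limits the point. It does not fill the gap: the one written method leaves the one stated obstacle untouched.

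**Conclusion.** The point holds in a limited form. The plan has no written procedure that keeps the dropper shape from the subject, so the single masking it claims is not assured, and some subjects could work out which product is which. Whether they would, how many, and which way it would move acuity are not known from the documents.

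The range of about 5% to 28% error at the margin, against a nominal 2.5%, is an illustration. It rests on an assumed average bias of 0.002 to 0.01 logMAR favouring test, the plan's covariance, 76 eyes with independent differences, and a normal approximation. It shows that a shift small against the 0.05 margin is not small against the standard error; it does not predict what will happen. This is a cheap improvement to the conduct of the trial and does not show that the primary result would be invalid.

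**What to change.** In section 5.2 and steps 1.18 and 1.25, require that:

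- the bottle is opened and the first drop discarded out of the subject's sight;
- the drop is instilled from an opaque sleeve, or with the subject's gaze averted so that the dropper is not seen;
- staff do not disclose product identity to the subject. The procedures already use neutral drop numbers, so only the instruction on disclosure is new.

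Section 5.2 should also say that the over-label alone is not the mask.

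The cost is a few sentences, inexpensive sleeves if that option is chosen, and slight extra handling. It needs no added staff, visits or assessments, and leaves the number and timing of drops as written. If sites already work this way, writing it down makes the practice uniform across up to three sites and open to monitoring. It does not remove the bias that may come from unmasked staff recording acuity, which needs separate consideration.

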#### 5.3. Procedures for Maintaining and Breaking the Masking

Under normal circumstances, the mask should not be broken until all subjects have completed the study and the database is finalized. Otherwise, the mask should be broken only if specific emergency treatment/course of action would be dictated by knowing the treatment status of the subject. In such cases, the investigator may, in an emergency, contact the medical monitor. In the event the mask is broken, the sponsor must be informed as soon as possible. The date, time, and reason for the unmasking must be documented in the subject record. The investigator is also advised not to reveal the study treatment assignment to the clinical site or sponsor personnel.

Subjects who are discontinued prior to the final evaluation may be replaced at the discretion of the study sponsor.

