#### 6.7. Accountability of Test Articles

JJVC will provide the Investigator with sufficient quantities of study articles and supplies to complete the investigation. The Investigator is asked to retain all test article shipment documentation for the test article accountability records.

Test articles must be kept in a locked storage cabinet, accessible only to those assigned by the Investigator for dispensing. The Investigator may delegate this activity to authorized study site personnel listed on the Site Delegation Log. All test articles must be accounted. This includes:

- 1. What was dispensed in-office for the subject.
- 2. What was unused, including expired or malfunctioning product.
- 3. The number and reason for unplanned replacements.

The Investigator will collect all unused test articles from the subjects at the end of the subject's participation. Inoffice dispensed or used test articles must be discarded or at least separated from the clinical study inventory of un-dispensed test articles and must be labeled with the subject number and date of return, when retained. Following final reconciliation of test articles by the monitor, the Investigator or monitor will return all unused test articles to JJVC.

If there is a discrepancy between the shipment documents and the contents, contact the study monitor immediately.

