1.22	10-minute Distance ETDRS LogMAR Visual Acuity (From OD Drop #1 Administration Time)	Under high illumination and high chart luminance, record the distance (4 meter) ETDRS low contrast visual acuity OD (LC1) and OS (LC2).		

	Visit 1: Treatment 1			
Step	Procedure	Details		
1.23	Habitual Contact Lens Fit Assessment Following the Application of Drop #1	
 
Evaluate and grade lens centration, primary gaze movement, up-gaze movement, and tightness (push-up test).
 
The subject should not proceed to wear the lenses if any of the following is observed: 
 
presence of limbal exposure (appearance of clear cornea) in any gaze
 
presence of edge lift
 
presence of unacceptable movement (excessive or insufficient) in all three movement categories (primary gaze, up-gaze, and push-up)
 
 
 
NOTE: If lens fit is unacceptable subject will be discontinued from the study.
 
		
1.24	Washout	Allow at least 90 minutes before continuing to the second drop as per the randomization schedule. (Subject will continue to wear their habitual lenses during this period.)		

	Visit 1: Treatment 2			
Step	tep Procedure Details			
1.25	Drop Instillation	The investigator will break the seal of Drop #2 and discard the first drop. The investigator or technician will instill 1 drop in the right eye. Wait 1 minute and then instill 1 drop in the left eye.		
1.26	Subject Reported Ocular Symptoms	Subjects will respond to a verbal open-ended symptoms questionnaire.		
1.27	Drop Settling	Allow the drops to settle for 3 minutes (from OD drop #2 administration).		
1.28	3-minute Distance ETDRS LogMAR Visual Acuity (From OD Drop #2 Administration Time)	Under high illumination and high chart luminance, record the distance (4 meter) ETDRS low contrast visual acuity OD (LC3) and OS (LC4).		
1.29	10-minute Distance ETDRS LogMAR Visual Acuity (From OD Drop #2 Administration Time)	Under high illumination and high chart luminance, record the distance (4 meter) ETDRS low contrast visual acuity OD (LC1) and OS (LC2).		

	Visit 1: Treatment 2			
Step	Procedure	Details		
1.30	Habitual Contact Lens Fit Assessment Following the Application of Drop #2	Evaluate and grade lens centration, primary gaze movement, up-gaze movement, and tightness (push-up test).		
		The subject should not proceed to wear the lenses if any of the following is observed:		

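### Should the person who runs the logMAR chart be masked, given that eyedropper shape is the only reason offered for leaving site staff unmasked?

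*Combined protocol and SAP*

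**What the plan says.** The synopsis and Sections 4.1 and 4.2 call the study single-masked. Section 5.2 gives the reason: "Due to the difference in the shape of the eyedroppers, double masking will not be possible". Subjects are masked by over-labelled bottles. For site staff the section is explicit: "Investigators and clinical site personnel involved in the data collection will not be masked as to the identity of the investigational product". It makes no exception for whoever records acuity.

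Other sections bear on who sees the bottle:

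- Section 6.7 on storage: "Test articles must be kept in a locked storage cabinet, accessible only to those assigned by the Investigator for dispensing". On delegation: "The Investigator may delegate this activity to authorized study site personnel listed on the Site Delegation Log".
- Section 7.2, step 1.18: "The investigator will break the seal of drop #1 and discard the first drop", and then "The investigator or technician will instill 1 drop in the right eye". Step 1.25 repeats this for the second period: "The investigator will break the seal of Drop #2 and discard the first drop".
- Section 5.3, after its instructions on emergency unmasking: "The investigator is also advised not to reveal the study treatment assignment to the clinical site or sponsor personnel".

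The acuity readings at 3 and 10 minutes (steps 1.21, 1.22, 1.28 and 1.29) are separate from instillation. They name no examiner and, as written, do not need the bottle. Section 14.5 tests non-inferiority on the 10-minute reading with a margin of 0.05 logMAR, and the study succeeds only if that test does.

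**The concern.** The reason is narrower than the exemption drawn from it. Bottle shape reveals the product to the person who handles the bottle. A colleague who comes in afterwards to run the chart could in principle remain unaware, and the protocol already has some of the parts for such a split: delegated dispensing, a technician who may instil, and at least three minutes between the right-eye drop and the first reading. Section 5.3 adds to the impression of a gap, because it appears to withhold from site staff what Section 5.2 says they know.

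The endpoint gives the point weight. Acuity on a chart is administered and recorded by a person. If knowing the product changed how hard the examiner pressed for another letter, the shift would follow the treatment. Within-subject comparison would not cancel it, and neither would the sequence and period terms, the ITT sensitivity analysis or multiple imputation. A shift toward Test could produce a false claim of non-inferiority; a shift against Test could cost the sponsor a true one.

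**Working it through.** **Inputs.** From Section 14.2: planning covariance matrix with variances 0.005117 and 0.005213 and covariance 0.003170; assumed true difference 0.025 (Test minus Control, higher is worse); 38 completers, both eyes measured, so 76 eyes; two-sided alpha 0.05; stated power 91% (Table 10). From Section 14.5: margin 0.05. The documents give no size for an examiner effect, so the shift b below is an assumption, positive when it favours Test.

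**Reproducing the plan's figure.**

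- Variance of a within-eye difference: 0.005117 + 0.005213 − 2 × 0.003170 = 0.00399.
- Standard error: √(0.00399 / 76) = 0.00725.
- Noncentrality: (0.05 − 0.025) / 0.00725 = 3.45.
- Power from the noncentral t distribution: 0.919 with 37 degrees of freedom, 0.926 with 74. Table 10 says 91%, so the planning figure is recovered to within two points.

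This treats the two eyes' differences as independent. With one eye per subject, power would be only 0.66 to 0.68, so the plan must be counting both eyes this way.

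**Adding a constant shift.** The chance of success is P = 1 − F(t₀.₉₇₅; df, (0.05 − d + b) / SE), where F is the noncentral t distribution function and d the true difference.

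| True difference d | Shift b | Chance of declaring non-inferiority (df 37 / 74) |
|---|---|---|
| 0.05 | 0 | 2.5% |
| 0.05 | +0.0023 | 5% |
| 0.025 | 0 | 91.9% / 92.6% |
| 0.025 | −0.0042 / −0.0044 | 80% |
| 0.01 | −0.01 | 98.1% / 98.3% |
| 0 | −0.01 | above 99.9% |

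Small shifts therefore matter at d = 0.05, and to a lesser degree at 0.025. They matter little at 0 or 0.01, where Test is truly non-inferior and a false claim cannot arise at all.

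**How firm these figures are.** Suppose the two eyes' differences correlate at 0.5 (an assumption; the documents give no value). Then SE = √(0.00399 × 1.5 / 76) = 0.00887.

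- At d = 0.025 with no shift, power is already 78% to 79%, so there is no fall from 92% to 80% left to attribute to an examiner.
- At d = 0.01 with b = −0.01, the chance of success is 91% to 92%, not 98%.
- The shift that doubles the 2.5% error at the margin becomes 0.0028 to 0.0029.

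**Which true difference is plausible.** Section 1 says Test contains the marketed formulation. Table 3 lists the same ingredients for both products except sodium chlorite, the preservative in Control. Table 9 shows a mean of 0.09 in both arms of the historical study, and Section 14.2 calls 0.025 conservative. All of this points to the low-impact rows, though it does not prove them.

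**The case for a change.** The strongest case for a change is that it looks nearly free. It would alter no sample size, alpha, model, visit or procedure. It protects the only endpoint that decides the study, and it protects in both directions. Where two delegated people are already present at instillation, one could run the chart without having seen the bottle or schedule; elsewhere the unmasked examiner would be reported as a limitation.

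Part of this stands: the stated reason does not reach a separate examiner, and the planned analyses could not detect or remove an examiner effect. The rest is weaker.

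- **Staffing.** The documents do not show it. Allowing either investigator or technician to instil does not establish that a second person is free at 3 and 10 minutes in both periods.
- **Uneven masking.** A rule that applies only where staffing permits would mix masked and unmasked readings across up to three sites, with no data field to tell them apart. It could neither be verified nor analysed.
- **Storage.** Section 6.7 is an accountability rule. It requires used articles to be discarded or kept apart from inventory; it does not clearly return the opened first bottle to the locked cabinet for the 90-minute washout.
- **Cost.** A revision would still need ethics review, delegation and training.
- **Seal-breaking and Section 5.3.** Who breaks the seal is irrelevant to an examiner who stays away from instillation. The Section 5.3 sentence follows directly on the emergency-unmasking steps and reads naturally as applying to that situation. It is loosely worded, but no result depends on it.

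**Conclusion.** No change is called for. Leaving the chart examiner unmasked is an openly declared trade-off, not an error or an omission. Subjects, who produce the responses, are masked. The visible procedures also limit examiner discretion: a set chart for each eye and time point, specified room illuminance and chart luminance, and timing limits on the right-eye readings in Table 8. How much discretion remains depends on the logMAR procedure in Appendix D, whose content is not readable in the public copy, so a small effect can be neither confirmed nor excluded.

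The size is unknown in both magnitude and direction. The break-even shifts of 0.0023 at the margin and 0.0042 to 0.0044 at the planned difference are illustrations. They assume a shift constant over subjects and sites and independent differences between eyes; under a between-eye correlation of 0.5 the second one disappears. With two near-identical formulations the likelier settings are those in which a shift of this order would not alter the conclusion. The single-masked design should be borne in mind when the result is read, and noting the unmasked examiner as a limitation in the study report is ordinary practice that needs no amendment.
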